8.1.2 Protocol Deviations

- Protocol deviation is defined as any unapproved change, deviation, or departure from the study design or procedures defined in the protocol.
- Major protocol deviation is defined as one that affects the integrity of the study data (integrity means completeness, accuracy and reliability of the data), and/or affects subject rights, safety or well-being. Major protocol deviations will be evaluated on a case-by-case basis. Categorization of protocol deviations will be reviewed periodically throughout the study, as well as before each formal analysis, by PPD and MannKind.
- Before study database lock, major protocol deviations related to study drug administration which impact subject eligibility in the PK Population will be identified, such as sneezing or coughing right after AFREZZA[®] inhalation on Day 1.
- All and major protocol violations will be summarized by category by cohort, as well as presented by a subject-level listing.

8.1.3 Subject Disposition

Number and percentage of subjects will be presented by cohort for the following categories:

- Screened Subjects
- Enrolled Subjects
- Safety Subjects
- PK subjects
- Subjects completed the titration period
- Subjects participated in the extension period
- Subjects completed the extension period
- Early Withdrawn Subjects during the titration period
- Early Withdrawn Subjects during the extension period

Detailed withdrawal reasons will be summarized separately for titration period and extension period and will also be presented in this table by cohort. Here is a summary of possible withdrawal reasons:

Version Date: 17-Jan-2020

- Adverse Event
- Death
- Lack of Efficacy
- Lost to Follow-up
- Non-Compliance with Study Drug
- Physician Decision
- Pregnancy
- Protocol Violation
- Study Terminated by Sponsor
- Subject begins Smoking
- Withdrawal by Subject
- Other

A detailed subject listing will also be presented.

8.2 PK Analyses

PK population will be used in all PK analyses.

At visit 2, PK blood samples as well as blood glucose values will be collected at multiple time points pre- and post-dose according to the table below:

Table 3 Schedule of the PK Visit Table

Day	D1																			
Time (minute)	-30	-25	-15	0	5	10	15	18	20	30	45	55	60	90	120	125	180	240	245	250
Indicative clock time	7:30 am	7:35 am	7:45 am	8:00 am	8:05 am	8:10 am	8:15 am	8:18 am	8:20 am	8:30 am	8:45 am	8:55 am	9:00 am	9:30 am	10:00 am	10:05 am	11:00 am	12:00 pm	12:05 pm	12:10 pm
Blood glucose via glucose meter reading ^a	X																			
Glucose value via local or central laboratory ^b				G00						G01			G02	G03	G04		G05	G06		
Study treatment administration																				
AFREZZA [®] inhalation				X ^c																X ^e
Meal				X ^d																X ^e
Pharmacokinetics																				
Human insulin	S00		S01	S02	S03	S04	S05		S06	S07	S08		S09	S10	S11		S12	S13		
FDKP				SF00			SF01				SF02				SF03				SF04	
Abbreviations: FEV ₁ , forced expiratory volume in 1 second; FDKP, fumaryl diketopiperazine; 
a. If the FPG value is ≥80 mg/dL at Visit 2, the subject will undergo a 4-hour PK assessment after eating his/her usual breakfast and receiving his/her breakfast dose of AFREZZA[®].
 
b. Glucose value via local or central laboratory: glucose reading to be done locally via a table top glucose meter (e.g., YSI) at Investigator site. Central laboratory will be used only if local reading (i.e., table top glucose meter) is not available.
 
c. Subject will inhale a dose of AFREZZA[®] under the supervision of the Investigator after the glucose sample has been taken and immediately before the first mouthful of food. The AFREZZA[®] dose will be calculated based on the conversion table. The AFREZZA[®] dosing time will be recorded in the electronic case report form (e-CRF).
 
d. Subject will receive a breakfast containing a predetermined level of carbohydrate, comprising approximately 50% of the total caloric content. The starting and ending time of breakfast will be recorded in the e-CRF.
 
e. At the conclusion of the PK test, plasma glucose concentration will be assessed and subjects will receive a lunch. The lunch should correspond in size and composition to the subject's usual lunch, and should be accompanied by an AFREZZA[®] dose corresponding to the subject's usual dose of prandial insulin with an adjustment (if necessary) based on the results of the glucose profile during the PK test and the pre-lunch plasma glucose value.
																				

PK parameters, as well as baseline-corrected insulin PK concentrations, will be computed by MannKind. The calculation methods will be described in a separate document (PK Analysis Plan for MKC-TI-155 Part 1).

The parameters will include, but may not be limited to, the following:

- Insulin C_{\max} (maximum observed concentration after correction for baseline)
- Insulin $AUC_{0-t_{\text{last}}}$ (area under the baseline-corrected concentration-time curve from time 0 to the last measurable concentration)
- Insulin t_{\max} (time to reach C_{\max})
- Apparent total body clearance (CL/F) and apparent volume of distribution (Vss/F) of insulin
- FDKP elimination half-life ($t_{1/2}$)
- Insulin AUC (area under the serum concentration versus time curve extrapolated to infinity) according to the following equation:

$$AUC = AUC_{\text{last}} + C_{\text{last}}/\lambda_z$$

In summary tables/figures, concentrations below limit of quantification (BLQ) will be imputed as $\frac{1}{2} * \text{Lower Limit of Quantification (LLQ)}$. In subject-listings, these values will be presented as BLQ

Table presentation

Baseline-corrected insulin concentrations and concentrations of FDKP will be summarized by PK dose, nominal time point and cohort. The number of subjects, mean, SD, geometric mean, CV, median, minimum, and maximum values will be displayed. Each PK parameter will be summarized by PK dose and cohort. In addition to the aforementioned descriptive statistics, 95% CI of the geometric mean will also be computed and presented, based on assumption of log-normal distribution of the parameters.

Blood glucose values and change from baseline (defined as the glucose value collected at 0 min pre-dose) will be summarized and presented by nominal time point and cohort.

Graphical Presentation

Mean +/- Standard error (SE) of baseline-corrected insulin concentrations and concentrations of FDKP will be plotted against nominal time by PK dose and cohort. In addition, individual patient profile plot of concentration vs. actual time will also be provided.

Blood glucose values collected at the PK visit will be plotted against nominal time by cohort. Similar individual patient plot will be created.

Subject Listings

PK concentrations and PK parameters for insulin and FDKP, as well as blood glucose values measured at PK visit, will be listed by (in the order of) cohort, PK dose, investigator site, and subject.

8.3 Safety Analyses

8.3.1 Adverse Event

Definition

Adverse Event (AE)

An AE is any untoward medical occurrence in a subject administered a pharmaceutical product and which does not necessarily have to have a causal relationship with this treatment. An AE can be any unfavorable and unintended sign (e.g., an abnormal laboratory finding), symptom, or disease temporally associated with the use of a drug, and does not imply any judgment about causality.

General

All adverse events will be described with cohort, start date, resolution date, seriousness, severity (mild, moderate, severe), outcome of AE (recovered/resolved, recovering/ resolving, recovered/resolved with sequelae, not recovered/resolved, death related to AE, and unknown), relationship to study treatment (definite, probable, possible, unlikely, and not related), action taken with investigational medicinal product (dose increased dose, dose not changed, dose reduced, dose interrupted, dose withdrawn, not applicable, and unknown), other action taken (treatment given and withdrawn from the trial).

Coding

Adverse events will be coded by the system organ class and preferred terms specified in the MedDRA (version 20.1) dictionary.

Classification

Prior Adverse Event

A prior adverse event is defined as adverse event whose start date is before the date of the first dose of study drug.

A subject listing will be presented for all the prior adverse events.

Treatment-Emergent Adverse Event (TEAE)

An adverse event is treatment-emergent if the start date is on or between the date of the first dose of study drug and the date of the last dose of study drug plus 30 days (inclusive). Worsening of a pre-treatment event during the trial is also treatment emergent.

Follow-up Adverse Event

A follow-up adverse event is defined as adverse event whose start date is between the date of the last dose of study drug plus 30 days (exclusive) and the date of the last visit day of the follow-up period.

A subject listing will be presented for all the follow-up adverse events.

Special Adverse Event

The following special treatment-emergent adverse event will be identified and reported from the adverse event database.

- Acute bronchospasm
- Verified clinically relevant decline in pulmonary function
- Hypersensitivity reactions, including anaphylaxis, which can occur with insulin products, including AFREZZA
- Diabetic ketoacidosis

Serious Adverse Event

A serious adverse event (SAE) is any untoward medical occurrence that suggests a significant hazard or side effect, regardless of the Investigator or sponsor's opinion of the relationship to the IMP, study related procedures or device. This includes, but is not limited to an event that:

- Is fatal;
- Is life threatening (places the trial subject at immediate risk of death);
- Requires in-patient hospitalization or prolongation of existing hospitalization;
- Results in a persistent or significant disability/incapacity;
- Is a congenital anomaly/birth defect; or
- Is an important medical event*

* Important medical events are those events that may not be immediately life threatening or result in death or hospitalization but may jeopardize the trial subject or require intervention to prevent one of the outcomes listed above. Examples include allergic bronchospasm, convulsions, and blood dyscrasias.

Most Common Treatment-Emergent Adverse Event

Most common treatment-emergent adverse events are defined as the TEAEs which occurred in $\geq 5\%$ subjects in any cohort during the entire study.

Table Presentation

Summary tables will be reported by cohort and study period (titration period, extension period, and entire study). Number and percentage of subjects with Aes, number of Aes and event rate in person-year accounting for the observation time will be presented for the following categories:

- Overall summary including: all TEAEs, drug-related TEAEs, serious TEAEs, drug-related serious TEAEs, severe TEAEs, moderate TEAEs, mild TEAEs, TEAEs leading to subject discontinuation from the trial, and TEAEs leading to death
- TEAEs by system organ class and preferred term
- TEAEs by preferred term only
- TEAEs by relationship to study drug by system organ class and preferred term
- TEAEs by severity by system organ class and preferred term
- Most Common TEAEs by system organ class and preferred term
- Serious TEAEs by system organ class and preferred term
- Serious TEAEs by relationship to study drug by system organ class and preferred term
- TEAEs leading to discontinuation by system organ class and preferred term
- TEAEs leading to death by system organ class and preferred term
- TEAEs leading to temporary treatment interruption by system organ class and preferred term
- TEAEs of special interest by system organ class and preferred term
- TEAEs of special interest by relationship to study drug by system organ class and preferred term

For percentage calculation, number of subjects in each cohort in the safety population will be used as denominator for the summaries for the entire study and the titration period. For the extension period, number of subjects in safety population who participate in extension period (see definition in Section 5.4) will be used as denominator.

Observation time for TEAE is defined as:

Version Date: 17-Jan-2020

- For the entire study: min(last visit/contact date, last dose date +30) – Study Day 1 + 1
- For the titration period:
 - min(last visit/contact date, last dose date +30) – Study Day 1 + 1, for subjects who do not participate in the extension period
 - date of Visit 15 – Study Day 1 +1, for subjects who participate in the extension study
- For the extension period: min(last visit/contact date, last dose date +30) – date of Visit 15, for subjects who participate in the extension period only.

Subject Listing

Individual data listings will be provided for the following, by (in the order of) cohort, investigator site and subject:

- All adverse events
- Treatment emergent adverse events
- Prior adverse events and follow-up adverse events
- Serious treatment-emergent adverse events
- Treatment-emergent adverse events leading to discontinuation from the trial
- Treatment-emergent adverse events leading to death
- Treatment-emergent adverse events leading to temporary treatment interruption
- Treatment-emergent adverse events of special interest

8.3.2 Deaths

Any deaths occurred in the trial will be reported. An individual subject listing will also be presented with details of death listed, by (in the order of) cohort, investigator site and subject.

8.3.3 Hypoglycemic Event

Definitions:

Hypoglycemic event:

The general symptoms of hypoglycemia most subjects experience include 1 or more of the following: headache, dizziness, general feeling of weakness, drowsiness, confusion, pallor, irritability, trembling, sweating, lightheadedness, shaky, increased appetite, rapid heartbeat and a

cold, clammy feeling. In severe cases, seizure, loss of consciousness, or even coma can occur.

All hypoglycemic events will be recorded on the Hypoglycemia eCRF page. In addition, severe hypoglycemia episodes and other hypoglycemia episodes which meet the criteria of SAE will also be records as SAEs in the AE page and safety complementary e-CRF.

Non-severe Hypoglycemic event

Non-severe hypoglycemic event is defined according to the ISPAD Clinical Practice Consensus Guidelines 2014 (3) as follows:

- SMBG levels <70 mg/dL and/or
- Symptoms of hypoglycemia that are relieved by the administration of carbohydrates

Severe Hypoglycemic event

Severe hypoglycemic event in children is defined according to the ISPAD Clinical Practice Consensus Guidelines 2014 (3) as an event associated with a seizure, coma, or loss of consciousness and will be considered an SAE.

Asymptomatic Hypoglycemic event

Asymptomatic hypoglycemic event is defined as an episode not accompanied by typical symptoms of hypoglycemia, but with a measured plasma glucose concentration < 70 mg/dL

Symptomatic hypoglycemic event

Symptomatic hypoglycemic event is defined as an episode accompanied with typical symptoms of hypoglycemia, with or without measured plasma glucose concentration, which is relieved by the administration of carbohydrates

Nocturnal hypoglycemic event

Nocturnal hypoglycemic event is defined as a hypoglycemia episode which occurs overnight during sleep.

Documented hypoglycemic event

Documented hypoglycemic event is defined as an episode with measured plasma glucose concentration <70 mg/dL. If such an episode is also accompanied by typical hypoglycemic symptoms, then it is defined as a symptomatic documented hypoglycemic event; otherwise, it is defined as an asymptomatic documented hypoglycemic event.

Table Presentation

Summary tables will be reported by cohort and study period (titration period, extension period, and entire study). Only hypoglycemic events occurred on treatment (i.e., with start date between the first dose date and last dose date, both inclusive) will be included. Number and percentage of subjects with hypoglycemic events, number of hypoglycemic events, and event rate in subject-month accounting for observation time will be presented for the following categories:

- All hypoglycemic events
- Asymptomatic hypoglycemic events
- Symptomatic hypoglycemic events
- Nocturnal hypoglycemic events
- Severe hypoglycemic events
- Documented hypoglycemic events
- Symptomatic documented hypoglycemic events
- Asymptomatic documented hypoglycemic events

For percentage calculation, number of subjects in each cohort in the safety population will be used as denominator for the summaries for the entire study and the titration period. For the extension period, number of subjects in safety population who participate in extension period will be used as denominator.

For calculation of event rate, observation time is defined as treatment exposure time (total exposure time and period-specific exposure time for the corresponding analysis respectively, see definition in Section 5.5).

In addition, causality of hypoglycemic events will be summarized (for the entire study only). Number and percentage of subjects experiencing hypoglycemic events in each causality category will be presented by cohort.

Graphical Presentation

Only hypoglycemic events occurred on treatment will be included. The following graphs will be presented by cohort and overall:

- Day profile of hypoglycemic events

Event rate (in subject-month) will be calculated at 1 week interval for the titration period and at 1 month interval the extension period, and plotted against time since the start of the study period. Onset date of the event will be used to determine the time interval. Weeks since the start of the study period will be calculated as $\text{int}((\text{date} - \text{start date of the study period} + 1) / 7)$. Months since the start of the period will be calculated as $\text{int}((\text{date} - \text{start date of the study period} + 1) / 30.4375)$.

The last interval in each study period, i.e., Week 4 for the titration period and Month 12 for the extension period, will extend to the treatment end date of the study period, for subjects whose treatment duration is longer than 4 weeks or 12 months, for the two study periods respectively.

To derive event rate, observation time (in months) for a time interval will be calculated as

The number of days in the time interval which are between first dose date and last dose date (both inclusive)/30.4375.

Observation time will first be calculated for each individual subject, and then summed across all applicable subjects in the safety population.

- Time profile of hypoglycemic events in relation to pre-meal dosing

For each week in the titration period and each month in the extension period, event rate of hypoglycemia (in subject-month) will be calculated at 1 hour interval (i.e., [0,1] h, (1,2) h, (2, 3) h, and (3, 4h)) relative to the pre-meal insulin dosing time. A bar plot will be created with hypoglycemic events occurred following each pre-meal dose presented as a separate bar. Only hypoglycemic events occurred within 4 hours following a pre-meal dose will be included in this analysis.

To derive event rate, observation time for an hour (e.g., 0-1 h after breakfast) in a time interval (e.g., Week 1 in titration period) will be calculated as

The number of days in the time interval which are between first dose date and last dose date (both inclusive) /30.4375.

Observation time will first be calculated for each individual subject, and then summed across all applicable subjects in the safety population.

Subject Listings

For all hypoglycemic events and all severe events, detailed information of every event will be listed, by (in the order of) cohort, investigator site and subject.

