10.2.4.2 Non-severe hypoglycemic episodes

Non-severe hypoglycemia is defined according to the ISPAD Clinical Practice Consensus Guidelines 2014 (10) as follows:

- SMBG levels <70 mg/dL and/or
- Symptoms of hypoglycemia that are relieved by the administration of carbohydrates

All episodes of hypoglycemia that meet this definition of non-severe hypoglycemia are to be recorded in the e-Diary, and will be reported on the hypoglycemia page in the e-CRF.

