10.2.4.3 Severe hypoglycemic episodes

Severe hypoglycemia in children is defined according to the ISPAD Clinical Practice Consensus Guidelines 2014 (10) as an event associated with a seizure, coma, or loss of consciousness and will be considered an SAE (see below). If glucose measurements are not available during such an event, the neurological recovery attributable to the restoration of glucose to normal will be considered sufficient evidence that the event was induced by a low glucose concentration.

The following episodes of hypoglycemia require reporting in the AE page and safety complementary e-CRFs and the hypoglycemia e-CRF. This applies for:

- Hypoglycemia associated with coma or loss of consciousness, or
- Hypoglycemic seizure, or
- Hypoglycemia that meets other conditions for an SAE, as defined under “Serious Adverse Event” in Section 10.2.2

The Investigator will adjudicate episodes of hypoglycemia reported in the e-Diary that appear to meet the criteria for SAEs. If the Investigator judges that the episode is not an SAE, it will be corrected on a data clarification form in the e-Diary and will not be recorded in an SAE e-CRF.

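### SAP 8.3.3 requires carbohydrate relief for a symptomatic hypoglycemic event but not for a symptomatic documented one, so some confirmed or severe episodes fall into neither the symptomatic nor the asymptomatic row

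*SAP*

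**What the plan says.** SAP 8.3.3 (Hypoglycemic Event) gives these definitions:

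- *Symptomatic*: an episode with typical symptoms, "with or without measured plasma glucose concentration, which is relieved by the administration of carbohydrates".
- *Documented*: "Documented hypoglycemic event is defined as an episode with measured plasma glucose concentration <70 mg/dL". The text continues: "If such an episode is also accompanied by typical hypoglycemic symptoms, then it is defined as a symptomatic documented hypoglycemic event". No relief condition is attached.
- *Asymptomatic*: "an episode not accompanied by typical symptoms of hypoglycemia, but with a measured plasma glucose concentration < 70 mg/dL".
- *Severe*: "an event associated with a seizure, coma, or loss of consciousness and will be considered an SAE". There is no glucose condition and no relief condition.

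The paragraph on symptoms that opens the section adds: "In severe cases, seizure, loss of consciousness, or even coma can occur".

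The same section tabulates all of these categories as separate rows, each with subjects, events and event rate, for on-treatment events (Table 14.3.2.1). SAP Appendix 3 marks that table for the DMC package.

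In Protocol 10.2.4.2, carbohydrate relief is one arm of an and/or definition of non-severe hypoglycemia. One arm is SMBG below 70 mg/dL. The other is "Symptoms of hypoglycemia that are relieved by the administration of carbohydrates". Asymptomatic, symptomatic, nocturnal and severe hypoglycemia are listed as safety endpoints in the protocol summary and in SAP 4.2.

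**The concern.** In the protocol, carbohydrate relief helps to identify a non-severe episode and is an alternative to a low reading. The SAP keeps that definition of non-severe hypoglycemia. It then also makes relief a condition of every symptomatic event, including those already confirmed by a value below 70 mg/dL and those that are severe. The condition is not repeated for symptomatic documented events.

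Two things follow if the definitions are programmed literally. First, *Symptomatic documented* is not contained in *Symptomatic*, although its name suggests that it is. Second, some episodes that are plainly symptomatic drop out of the symptomatic count and rate without entering the asymptomatic row. With planned cohorts of 18, 14 and 14 subjects, one or two such events could visibly change a row that the DMC sees.

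**Working it through.** The plan states no figure on this point, so the check is to classify every kind of episode by the literal definitions.

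**Inputs** (SAP 8.3.3): S = typical symptoms; G = measured glucose below 70 mg/dL; R = relieved by carbohydrates; V = seizure, coma or loss of consciousness.

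- *Symptomatic* = S and R
- *Symptomatic documented* = S and G
- *Asymptomatic* = G and not S
- *Severe* = V

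**Classification.** A severe event is taken to have symptoms, which is the natural reading of the paragraph on symptoms.

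| Episode | Symptomatic | Asymptomatic | Symptomatic documented | Severe |
|---|---|---|---|---|
| S, G, R, not severe | yes | no | yes | no |
| S, R, no G, not severe | yes | no | no | no |
| G, no S, not severe | no | yes | no | no |
| **S, G, no R, not severe** | **no** | **no** | **yes** | no |
| Severe, G, R | yes | no | yes | yes |
| Severe, R, no G | yes | no | no | yes |
| **Severe, G, no R** | **no** | **no** | **yes** | yes |
| **Severe, no G, no R** | **no** | **no** | **no** | yes |

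Three of the eight kinds are neither symptomatic nor asymptomatic. Two of those three are symptomatic documented.

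On a narrower reading, seizure, coma and loss of consciousness are not themselves typical symptoms. A severe event with a value below 70 and no listed symptom would then be classed as asymptomatic, which is also an anomaly.

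**When the rows invert.** Write n(·) for the number of events of a kind.

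- *Symptomatic documented* = n(S,G,R) + n(S,G,no R)
- *Symptomatic* = n(S,G,R) + n(S,R,no G)
- Difference = n(S,G,no R) − n(S,R,no G)

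The documented row exceeds the symptomatic row only when this difference is positive.

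**Illustration with hypothetical counts.** Take 10 symptomatic documented events, 2 of them not relieved by carbohydrates, and 1 carbohydrate-relieved symptomatic event without a value below 70. As written, *Symptomatic* = 10 − 2 + 1 = 9 against *Symptomatic documented* = 10. If relief is required only where no value below 70 was measured, *Symptomatic* = 10 + 1 = 11 against 10, and the rows nest.

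**After the proposed change**, *Symptomatic* = V, or S with (G or R). With V counted as a symptom, *Symptomatic documented* (S and G) always lies inside it. Every episode that meets the SAP's severe or non-severe definition then falls in exactly one of *Symptomatic* and *Asymptomatic*.

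**The case against.** The case on the other side has real force in several places.

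- **Parent row.** The SAP change log introduces the symptomatic and asymptomatic documented categories as subdivisions of documented hypoglycemia, a row they can never exceed. *Symptomatic* is the parent by name only. This stands. So does the point that an inversion is only possible, not predicted.
- **Nothing is lost.** Affected events still appear under all hypoglycemic events, in the severe row if severe, and in Listings 16.2.7.10 and 16.2.7.11 as applicable. Severe events are also reported as SAEs. This stands, and it limits the harm to the symptomatic/asymptomatic split.
- **Narrow gap.** Protocol 9.2.6.4 mentions carbohydrate intake and glucose administration together, so glucose-treated episodes can be read as carbohydrate-relieved. The gap then covers other corrective actions, which Protocol 10.2.4.1 names separately from carbohydrates when it describes the adult definition, and episodes that resolve untreated. This also stands. The documents give no frequency for either.
- **Unseen derivation.** The table shells are separate files and the hypoglycemia eCRF page is not among the documents, so the programmed rule may differ from the text.
- **Descriptive use.** No test, stopping threshold or cohort-progression rule in the documents uses the symptomatic row.

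None of this reconciles the two definitions.

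A reader might also infer three stronger points that the documents do not support:

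- **Missing recovery rule.** For severe events without a glucose value, Protocol 10.2.4.3 says that "the neurological recovery attributable to the restoration of glucose to normal will be considered sufficient evidence". The SAP does not repeat this. But its severe definition has no glucose condition, so the omission changes no count.
- **Symptoms at 70 mg/dL or above.** Counting them as symptomatic when carbohydrates relieve them may look like an SAP error. It follows the protocol's own and/or definition, and removing them would create another group in neither row.
- **Size from the adult rate.** The severe rate in Protocol 4.4 (5.63 per 100 subject-months) gives 0.0563 × 46 × 28/30.4375 = 2.38 events. That counts all severe events under an adult definition that the protocol itself regards as unsuitable for children. It does not count misclassified events.

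**Conclusion.** The definitions in SAP 8.3.3 are inconsistent as written. An episode with typical symptoms and glucose below 70 mg/dL that was not relieved by carbohydrates counts as symptomatic documented but as neither symptomatic nor asymptomatic. A severe event not relieved by carbohydrates and without a value below 70 is in neither row. The symptomatic count and rate can therefore omit confirmed or severe symptomatic episodes.

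The size is unknown: it is the number of such events, which the documents do not give and which may be small or zero. The conclusion rests on literal application of the definitions. The severe part also rests on reading seizure, coma and loss of consciousness as symptoms, or on there being no value below 70. It would be too strong to say that severe events disappear from the report, or that the documented row will exceed the symptomatic row.

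**What to change.** In SAP 8.3.3:

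1. Apply the carbohydrate-relief condition only to non-severe symptomatic episodes without a measured glucose below 70 mg/dL.
2. State that every episode with typical symptoms and a measured value below 70 mg/dL, and every severe event, counts as symptomatic. Say that seizure, coma and loss of consciousness count as symptoms in all of these definitions, so that no severe event can be classed as asymptomatic.
3. Keep carbohydrate-relieved symptoms without a value below 70 mg/dL in the symptomatic row, in line with Protocol 10.2.4.2.

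The cost is a short wording change and a revised derivation, with no new table row and, as far as the documents show, no new data. The table shells and eCRF fields should be checked against the revised text. Protocol 13 already allows the SAP to be amended. The change concerns classification for analysis only and implies no treatment rule.
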